#### **4.3 Alternatives**

The alternative to participation on this study is to receive allogeneic HCT on other clinical protocols or treatment plans without the use of maintenance ibrutinib. This alternative will be discussed with subjects during the informed consent process.

### **5. INVESTIGATIONAL AGENT INFORMATION**

#### **5.1 Investigational Agent**

The investigational agent utilized in this clinical trial is ibrutinib, administered at a dose of 420 mg orally once-a-day (with dose adjustments for concomitant medications or toxicity as described elsewhere in this protocol) and continued for 1 year, until disease progression, or until discontinuation due to adverse events. **EXCEPTION:** The starting dose for subjects with mild liver impairment (Child-Pugh Class A) is defined to be 140 mg/day.

Ibrutinib capsules are size 0, hard gelatin capsules for oral administration and contain 140 mg of micronized ibrutinib (content may be adjusted for water content and purity) and the following compendial excipients (National Formulary, Pharmacopoeia Europe, Japan Pharmacopoeia): microcrystalline cellulose; croscarmellose sodium; sodium lauryl sulfate; and magnesium stearate. Capsules are packaged in high-density polyethylene bottles with an induction seal and a child resistant screw-top cap. The number of capsules per bottle is indicated on the label.

Ibrutinib capsules should be stored according to the storage conditions indicated on the label. The recommended storage condition for ibrutinib capsules is 15° C to 25° C (59° F to 77° F) with excursions permitted to 30° C (86° F). Ibrutinib should be administered orally once daily with a glass of water at approximately the same time each day. The capsules should be swallowed whole with water and should not be opened, broken, or chewed. Ibrutinib must not be taken with grapefruit juice.

There are limited data on the effects of ibrutinib overdose. No maximum tolerated dose (MTD) was reached in the Phase 1 study in which subjects received up to 12.5 mg/kg/day (1400 mg). In a separate study, one healthy subject who received a dose of 1680 mg experienced reversible Grade 4 hepatic enzyme increases (AST and ALT). There is no specific antidote for ibrutinib. Subjects who ingested more than the recommended dosage should be closely monitored and given appropriate supportive treatment.

*For the most comprehensive information regarding ibrutinib, refer to the current version of the Investigator's Brochure.*

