EXCLUSION CRITERIA	
 
Active involvement of the central nervous system with malignancy (previous CNS involvement is allowed if clearance of CNS disease has been documented prior to enrollment)
 
Pregnant or breastfeeding
 
Karnofsky Performance Status < 60%
 
Active leukemia (> 5% leukemic blasts in peripheral blood or bone marrow)
 
Non-hematologic malignancy with a life expectancy of < 5 years
 
Known history of human immunodeficiency virus (HIV) or active hepatitis C virus (HCV) or hepatitis B virus (HBV) infection. Subjects who are positive for hepatitis B core antibody or hepatitis B surface antigen must have a negative polymerase chain reaction (PCR) result before enrollment. Those who are PCR-positive will be excluded.
 
Known bleeding disorders (eg, von Willebrand's disease) or hemophilia.
 
History of other malignancies, except: 
 
Malignancy treated with curative intent and with no known active disease present for <math>\geq</math> 3 years before the first dose of study drug and felt to be at low risk for recurrence by treating physician.
 
Adequately treated non-melanoma skin cancer or lentigo maligna without evidence of disease.
 
Adequately treated carcinoma in situ without evidence of disease.
 
 
 

TREATMENT SUMMARY	Subjects will be treated with ibrutinib 420 mg orally once daily, starting between Day +60 and Day +90 after allogeneic HCT and continuing until 18 months post-transplant
SAMPLE SIZE	50 subjects enrolled and treated
STATISTICAL CONSIDERATIONS	Screening and enrollment of 50 subjects will provide 84% power to detect a decrease in the incidence of relapse at 18 months post-transplant from 45% to 25%

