#### 4. TREATMENT PLAN

Subjects will be assessed for eligibility and enrolled prior to allogeneic HCT, using the pre-transplant inclusion and exclusion criteria above. Eligible and enrolled subjects will then be reassessed prior to the administration of ibrutinib, which may begin at any point between Day +60 and Day +90 after allogeneic HCT, using the pre-ibrutinib inclusion and exclusion criteria above. Ibrutinib will not be initiated until the enrollment checklist has been reviewed by the coordinating center; a minimum of 48 hours' notice is required.

If subjects are deemed ineligible prior to beginning ibrutinib therapy, they may be reassessed for eligibility at any point until Day +90 after allogeneic HCT, and ibrutinib may be initiated if they meet all relevant criteria at any point between Day +60 and Day +90 after allogeneic HCT. Subjects beyond Day +90 will not be eligible to initiate ibrutinib if they have not already done so.

**Pre-transplant screening: all studies to be completed within 60 days of beginning conditioning therapy, unless otherwise indicated:**

- History and physical examination, including Karnofsky Performance Status (**standard of care**)
- Serologic and/or nucleic-acid testing for HIV, hepatitis B, and hepatitis C according to institutional standard practice (**standard of care**)
- Serum pregnancy testing, for women of childbearing potential (**standard of care**)
- Bone marrow examination, including assessment of minimal residual disease by multiparameter flow cytometry or high-throughput sequencing (**standard of care**)
- Disease assessment (**standard of care**): Data forms for CIBMTR will be made available to the coordinating center. Alternatively, detailed disease assessment data will be entered directly into the electronic database.
- Complete enrollment checklist and submit to coordinating center for review prior to enrollment. Preparative regimen for HCT should not begin until enrollment checklist has been reviewed by coordinating center (**research**).

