**Start of preparative regimen through Day +60 to Day +90:**

- Pre-conditioning blood sample from HCT recipient for high-throughput sequencing, flow cytometry, and CyTOF (**research**)
- Blood sample from HCT donor (related only), as a baseline to investigate development of post-transplant GVL effects (**research**)
- Disease reassessment between Day +28 and Day +60, including bone marrow examination and assessment of minimal residual disease as described above (**standard of care**)

**Prior to administration of ibrutinib (Day +60 to Day +90; all studies should be done within 2 weeks of starting ibrutinib):**

- Laboratory assessment of hepatic and renal function (**standard of care**)
- Assessment of acute GvHD presence, severity, and therapy history (**standard of care**)

- History and physical, including Karnofsky Performance Status (**standard of care**)
- Assessment of concomitant medications (**standard of care**)
- Collection of peripheral blood samples for mixed lymphocyte reactions, Th1/Th2 assays, and other correlative science endpoints (**research**)

Ibrutinib will be initiated between Day +60 and Day +90, after confirmation that the subject meets all relevant eligibility criteria. The drug will be dosed, and doses modified, as described below. The following assessments will be performed after initiation of ibrutinib:

**After start of ibrutinib until 2 years post-transplant** (tests should be performed +/- 2 weeks of given time points through Day +180, and +/- 4 weeks of given timepoints after Day +180):

- History, physical examination, and laboratory assessment of hematologic and chemistry tests per institutional standard practice (**standard of care**)
- Acute GvHD assessment weekly through Day +100 (**standard of care**)
- Chronic GvHD assessment at 6 months, 9 months, 12 months, 15 months, 18 months, and 2 years post-transplant (**standard of care**)
- Toxicity assessment at baseline (before starting ibrutinib), weekly through Day +100, monthly until Day +180, and then at 9 months, 12 months, 15 months, and 18 months post-transplant (**research**), unless ibrutinib has been permanently discontinued

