#### **4.2 Criteria for Removal from Study**

Ibrutinib will be continued until 18 months post-transplant, or until one of the following occurs: disease relapse; or discontinuation due to adverse events. Subjects with leukemia relapse after allogeneic HCT will discontinue the study drug, and may be treated with any and all appropriate therapies, including investigational agents, at the discretion of the treating physician.

Subjects will be withdrawn from study treatment if one of the following occurs: leukemia relapse; unacceptable toxicity requiring interruption of ibrutinib for more than 28 continuous days; investigator decision; withdrawal of consent by the subject for further treatment and/or follow-up; pregnancy; or study termination. All enrolled subjects, regardless of discontinuation of study treatment, will be followed for leukemia relapse and survival until 18 months after allogeneic HCT unless the subject withdraws consent for follow-up.

Withdrawal from the study will occur under the following conditions: withdrawal of consent for follow-up observation by the subject; loss to follow-up; study termination; or death. When an enrolled subject withdraws from the study, the reason for withdrawal should be documented, as should the subject's willingness to participate in follow-up visits or assessments.

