- e. Other medical events that may not be immediately life-threatening or result in death or hospitalization but may jeopardize the subject or require intervention to prevent one of the outcomes listed above

Study subjects will be instructed to report any adverse events to investigators and subjects will be evaluated for adverse events at every clinic visit. All adverse events will be documented by investigators and will contain the following information, if known:

- a. Medical diagnosis of the event
- b. Date and time of onset of event
- c. Date and time of resolution of event
- d. Severity of the event according to the National Cancer Institute (NCI) Common Toxicity Criteria and Adverse Events (CTCAE) criteria, version 4.0
- e. Frequency of the event
- f. Intervention
- g. Outcome
- h. Likelihood of association between the event and the study drug

The following are NOT considered AEs:

- **Pre-existing condition:** A pre-existing condition (documented on the medical history CRF) is not considered an AE unless the severity, frequency, or character of the event worsens during the study period.
- **Pre-planned or elective hospitalization:** A hospitalization planned before signing the informed consent form is not considered an SAE, but rather a therapeutic intervention. However, if during the pre-planned hospitalization an event occurs, which prolongs the hospitalization or meets any other SAE criteria, the event will be considered an SAE. Surgeries or interventions that were under consideration, but not performed before enrollment in the study, will not be considered serious if they are performed after enrollment in the study for a condition that has not changed from its baseline level. Elective hospitalizations for social reasons, solely for the administration of chemotherapy, or due to long travel distances are also not SAEs.
- **Diagnostic Testing and Procedures:** Testing and procedures should not to be reported as AEs or SAEs, but rather the cause for the test or procedure should be reported.

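### Section 5.1 continues ibrutinib for 1 year, but the synopsis and Section 4.2 continue it until 18 months post-transplant; no permitted start date satisfies both

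*Combined protocol and SAP*

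**What the plan says.** Two durations stand in the current text.

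- **Section 5.1 (Investigational Agent).** The sentence that sets 420 mg once daily goes on "and continued for 1 year, until disease progression, or until discontinuation due to adverse events".
- **Section 4.2 (Criteria for Removal from Study).** "Ibrutinib will be continued until 18 months post-transplant, or until one of the following occurs"; relapse and adverse-event discontinuation follow.
- **Synopsis, Treatment Summary.** Dosing starts between Day +60 and Day +90, "continuing until 18 months post-transplant".

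Three other provisions bear on the point. Section 4 fixes the start of ibrutinib, "which may begin at any point between Day +60 and Day +90 after allogeneic HCT", and bars a first dose after Day +90. The toxicity schedule in Section 4 is weekly, then monthly, "and then at 9 months, 12 months, 15 months, and 18 months post-transplant", with the condition "unless ibrutinib has been permanently discontinued". Section 7.2 adds that "subjects will be evaluated for adverse events at every clinic visit".

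**The concern.** The three statements agree on early stopping for relapse or progression and for adverse events. They differ on the planned end of treatment for a subject who is still taking the drug. Section 5.1 is an operative dosing sentence, and a pharmacist or site coordinator could reasonably take the duration from it. Section 12.4 plans three centers, so sites could apply different durations.

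At stake is the length of the intervention under test, and with it anything counted from the last dose. Examples are the contraception periods in Section 3.1.2 (30 days for females, 90 for males) and the 90-day death-reporting period after allogeneic transplant in Section 7.2. The dedicated toxicity visits may also be affected, because they are tied to whether ibrutinib has been permanently stopped.

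**Working it through.** **Inputs.** First dose from Day +60 to Day +90 (synopsis, Section 4). Stop at 18 months post-transplant (synopsis, Section 4.2). Stop after 1 year (Section 5.1), taken as 365 days from first dose. Month length is taken as 365.25 / 12 = 30.4375 days, so 18 months = 18 x 30.4375 = 547.9, about Day 548.

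**Step 1. Can the 1-year figure be recovered from the start window and the 18-month stop?** Duration = 548 - start day.
- Start Day +60: 548 - 60 = 488 days (16.0 months).
- Start Day +90: 548 - 90 = 458 days (15.0 months).

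Neither is 365. A 365-day course ending at month 18 would need a first dose at 548 - 365 = Day +183, which is 93 days past the Day +90 limit.

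**Step 2. Where does a 1-year course end?** Stop day = start day + 365.

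| Start | 1-year stop | Days before Day 548 | Days on drug, 5.1 vs 4.2 | Fewer treatment days |
|---|---|---|---|---|
| Day +60 | Day 425 | 123 | 365 vs 488 | 1 - 365/488 = 25.2% |
| Day +90 | Day 455 | 93 | 365 vs 458 | 1 - 365/458 = 20.3% |

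**Step 3. Does month length explain it?** No. With 30-day months, month 18 is Day 540 and the gap is 85 to 115 days. With 31-day months it is Day 558 and the gap is 103 to 133 days.

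**Step 4. Do visit windows explain it?** No. The tolerance ("4 weeks of given timepoints after Day +180") applies to tests, not to dosing. Even if it were applied to the stopping date, 548 - 28 = Day 520 is still 65 days after the latest 1-year stop.

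**Step 5. Does counting the year from transplant help?** No. Treatment would end at Day 365, about 183 days before month 18.

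**Step 6. Does the sample-size calculation depend on duration?** No. Its inputs are 45%, 25%, n = 50 and two-sided 0.05. An exact binomial test (reject at 15 or fewer relapses) gives 83.7%, matching the stated 84%. For n = 45 it gives 78.4%, matching the stated 78%. Treatment length enters neither figure.

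**The case against.** The strongest reply is that a careful reader would not be misled. Section 5.1 sits among capsule, storage and overdose information. The stopping rule proper is in the Treatment Plan (Section 4.2), the synopsis repeats it, and the toxicity schedule runs to the same point. In the Section 9 calendar the ibrutinib row also appears to close at 18 months, although its column alignment is unreliable. On this view Section 5.1 holds a leftover phrase and the protocol is not evenly split. That stands as to which duration is intended. It does not make Section 5.1 correct: the phrase shares a sentence with the dose, and nothing tells a site which section governs.

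A reader might also infer more than the documents support.

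- **That the 18-month toxicity assessment would be lost.** This requires completing a planned course to count as permanent discontinuation, which the protocol does not say. Section 6.1 uses the term for toxicity-driven stopping. On that reading a subject who completes a year keeps the later assessments. Adverse events are in any case evaluated at every clinic visit, and the calendar's adverse-event row appears to run to 2 years.
- **That 20-25% less drug would be given.** The figure counts days. Section 6 expects most subjects to be on azoles until at least Day +75, with ibrutinib at 140 mg meanwhile, so days do not translate directly into dose.
- **That the primary analysis is compromised.** Section 4.2 follows all enrolled subjects for relapse and survival to 18 months whether or not they stop drug, unless they withdraw consent for follow-up. Section 12.3 analyzes them by intention to treat.

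**Conclusion.** The inconsistency is real and should be fixed. Section 5.1 is wrong as written if the synopsis and Section 4.2 state the intent, as the weight of the text indicates. For a subject who completes planned dosing, the two rules differ by 93 to 123 days, or 20-25% of the 18-month rule's treatment days, and no permitted start date reconciles them. This rests on counting the year from first dose, the natural reading, and on average-length months; other month lengths or counting from transplant leave the conflict in place.

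The practical consequence is that a site following Section 5.1 would stop drug 3 to 4 months early. Whether the dedicated 18-month toxicity assessment would then be required is unclear rather than settled. The stated power, the endpoint definition and the analysis population do not change. No effect of a shorter course on the relapse rate can be computed from the documents.

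**What to change.** In Section 5.1, replace the one-year duration with the synopsis wording, "continuing until 18 months post-transplant", leaving the early-stopping conditions as they are. This brings Section 5.1 into line with Section 4.2 and the toxicity schedule. The cost is one phrase in a protocol amendment, with no change to sample size, endpoint, visits or analysis.

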## **Pharmacology**

Ibrutinib was designed as a selective and covalent inhibitor of Bruton's tyrosine kinase (17). *In vitro*, ibrutinib is a potent inhibitor of Btk activity (IC50 = 0.39 nM). The irreversible binding of ibrutinib to cysteine-481 in the active site of Btk results in sustained inhibition of Btk catalytic activity and enhanced selectivity over other kinases that do not contain a cysteine at this position. When added directly to human whole blood, ibrutinib inhibits signal transduction from the B-cell receptor and blocks primary B-cell activation (IC50 = 80 nM) as assayed by anti-IgM stimulation followed by CD69 expression (18).

Ibrutinib arrested cell growth and induced apoptosis in human B-cell lymphoma cell lines *in vitro* and inhibited tumor growth *in vivo* in xenograft models (18). Ibrutinib also inhibited adhesion and migration of mantle cell lymphoma (MCL) cells in co-culture and reduced tumor burden in lymph node and bone marrow in a murine model of MCL dissemination and progression (19).

## **Toxicology**

In safety pharmacology assessments, no treatment-related effects were observed in the central nervous system or respiratory system in rats at any dose tested. Further, no treatment-related corrected QT interval (QTc) prolongation effect was observed at any tested dose in a cardiovascular study using telemetry-monitored dogs.

Based on data from rat and dog including general toxicity studies up to 13 weeks duration, the greatest potential for human toxicity with ibrutinib is predicted to be in lymphoid tissues (lymphoid depletion) and the gastrointestinal tract (soft feces/diarrhea with or without inflammation). Additional toxicity findings seen in only one species with no observed human correlate in clinical studies to date include pancreatic acinar cell

atrophy (rat), minimally decreased trabecular and cortical bone (rat) and corneal dystrophy (dog).

In vitro and in vivo genetic toxicity studies showed that ibrutinib is not genotoxic. In a rat embryo-fetal toxicity study ibrutinib administration was associated with fetal loss and malformations (teratogenicity) at ibrutinib doses that result in approximately 6 times and 14 times the exposure (AUC) in subjects administered the dose of 420 and 560 mg daily, respectively.

### **Carcinogenesis, Mutagenesis, Impairment of Fertility**

Carcinogenicity studies have not been conducted with ibrutinib. Ibrutinib was not mutagenic in a bacterial mutagenicity (Ames) assay, was not clastogenic in a chromosome aberration assay in mammalian (CHO) cells, nor was it clastogenic in an in vivo bone marrow micronucleus assay in mice at doses up to 2000 mg/kg. Fertility studies with ibrutinib have not been conducted in animals. In the general toxicology studies conducted in rats and dogs, orally administered ibrutinib did not result in adverse effects on reproductive organs.

### **Pharmacokinetics and Metabolism**

Following oral administration of ibrutinib at doses ranging from 1.25 to 12.5 mg/kg/day as well as fixed dose levels of 420, 560, and 840 mg/day, exposure to ibrutinib increased as doses increased with substantial intersubject variability. The mean half-life ( $t_{1/2}$ ) of ibrutinib across 3 clinical studies ranged from 4 to 9 hours, with a median time to maximum plasma concentration ( $T_{max}$ ) of 2 hours. Administration of 420 mg ibrutinib with a high-fat breakfast in subjects with CLL approximately doubled the mean systemic exposure compared to intake after overnight fasting with median time to  $T_{max}$  delayed from 2 to 4 hours. Ibrutinib was extensively metabolized to the dihydrodiol metabolite PCI-45227, a reversible inhibitor of Btk, with approximately 15-times lower inhibitory potency compared to ibrutinib. The metabolite-to-parent AUC ratio ranged from 0.7 to 3.4. Steady-state exposure of ibrutinib and PCI-45227 was less than 2-fold of first dose exposure.

The results of human mass balance study of [ $^{14}C$ ]-ibrutinib conducted in six healthy male subjects demonstrated that less than 10% of the total dose of [ $^{14}C$ ]-ibrutinib is renally excreted, whereas approximately 80% is recovered in feces. Subjects with mild and moderate renal insufficiency (creatinine clearance  $> 30$  mL/min) were eligible to enroll in Study PCYC-1102-CA in which pharmacokinetic (PK) assessments were included. No dose adjustment is needed for mild or moderate renal impairment (greater than 30 mL/min creatinine clearance). There is no data in subjects with severe renal impairment or subjects on dialysis. The study of ibrutinib in hepatic impaired subjects is currently in progress.

## Summary of Clinical Safety

Pooled safety data for a total of 1071 subjects treated with ibrutinib monotherapy from 9 studies in B-cell malignancies, which includes subjects from 2 randomized-control studies who crossed over from comparator treatment or placebo to receive ibrutinib monotherapy, are summarized below in Table 1.

**Table 1. Most frequently reported treatment-emergent adverse events (TEAEs) in subjects receiving ibrutinib as monotherapy (N=1071):**

Most frequently reported TEAEs > 10%	Most frequently reported Grade 3 or 4 TEAEs > 2%	Most frequently reported Serious TEAEs > 1%
Diarrhea	Neutropenia	Pneumonia
Fatigue	Pneumonia	Atrial fibrillation
Nausea	Thrombocytopenia	Febrile neutropenia
Cough	Anemia	Pyrexia
Anemia	Hypertension	
Pyrexia	Atrial fibrillation	
Neutropenia		

For more detailed information refer to the current version of the IB.

